Efficacy of Platelet Enriched Plasma in preventing surgery for patients with chronic tympanic membrane perforation

Protocol Version 3; February 7th; January 22, 2018

Background & Rationale

Tympanic membrane (TM) perforation is the leading cause of conductive hearing loss. TM perforations in adults typically arise from middle ear infections, trauma, or from iatrogenic cause. While approximately 80% TM perforations close with time and conservative managements, approximately 20% require surgical intervention[1-3]. Often before exploring surgical options some patients opt for trial for paper patch myringoplasty that can be performed in the clinic. Success rates with paper patch myringoplasty are variable and can range from 12 to 63% depending on whether the size of the perforation is large or small[4]. When patients fail conservative treatment with paper patch, patients will explore surgical options. Surgical success rates for myringoplasty vary and quoted ranging from 60 - 90% in adults to 34-85% in children, and often lower in anterior TM perforations secondary to more difficult exposure[1]. Of those patients that do require surgical intervention, costs of tympanoplasty can cost upwards of twenty-four thousand dollars[5].

Multiple different biologic materials have been heavily investigated in the literature including hyaluronic acid, heparin, epidermal growth factor, fibroblast growth factor, platelet derived growth factor, and transforming growth factor with variable success[6]. Recently platelet enriched plasma (PRP) has been favored in multiple surgical procedures from orthopedics, ENT, to plastic surgery[7, 8]. The rationale behind its use are two fold; first platelets play a fundamental role in hemostasis and wound healing, and secondly the alpha granules contained within platelets contain various growth factors that play a fundamental role in wound healing[9]. Currently there are three different PRP that are FDA approved, SMARTPEP (SmartPEP, Harvest Technologies Corp, Norwell, MA) and Platelet Concentrating Collection Systems (3i/Implant innovations, Palm Beach Gardens, FL), and Arthrex (Arthrex Naples, FL) [2]. PRP is an autologous blood donation, where whole blood is collected from the patient and subsequently isolated through differential gradient centrifugation in an anticoagulant citrate dextrose-A[2].

PRP is widely used throughout multiple surgical subspecialties daily including Otolaryngology, Orthopedic surgery, Plastic surgery, Dermatology, OMFS, and Dentistry for over two decades. Despite its clinical advantages, to date there are no studies that have reliably investigated adverse events associated with PRP because of poor and inconsistent methodology[10]. However, there are intermittent case reports that report adverse events. A case report by Kaux *et al* (2014) found one adverse event out of 1000 injections performed. They reported one PRP injection into a 35-year-old male with diabetes caused an exuberant inflammatory reaction, characterized by swelling, pain, and erythema[11]. However, a large Cochrane data base review looking at PRP in musculoskeletal injuries examined over 19 trials covering over 1000 patients and found no difference in adverse events (including pain, infection, tendon rupture, and anaphylactic reaction) [12]. A separate systematic review examining six studies found no difference in complication rates between PRP and controls for acute muscle injuries (including hematoma, discomfort, hyperesthesia at injection site)[13]. Another Cochrane database review looking at PRP effectiveness for sinus lift procedures for dental implant rehabilitation examined over 29 trials and found no difference in complication rates or adverse events with PRP compared to controls (including sinusitis, infection, nerve injury, hematoma, perforation into sinus) [14].

Recently a study by Erkilet (2008) investigated the use of platelet enriched plasma (PRP) on 88 TM on 44 rats, treating one ear with PRP while the contralateral ear was left to heal spontaneously[9]. They

demonstrated that those tympanic membranes treated with PEP had faster healing times both clinically and on histopathology. In a separate study, acute TM perforations were created in rabbits and PRP was shown to significantly quicken time to heal without any difference on a microscopic level[15]. While PRP has been shown to be effective as sole treatment for animal models, it has yet to be investigated independently in humans. A study by El-Anwar (2015) looked at concurrent use of PRP with myringoplasty, which involves a post-auricular incision to inlay a medial TM graft, and found statistically improved graft take and healing[16]. However, the use in this case is in an intraoperative setting with an already established surgical procedure.

We wish to pursue and investigate the use of PRP in a clinical setting as the sole treatment for small tympanic membrane perforations. While no studies exist on the specific use of PRP as sole treatment modality, multiple studies have shown success with various growth factors such as PDGF and ECF[17]. PRP is promising because its ability to use a variety autologous growth factors stored within their alpha granules, negating the need for exogenous growth factors. Ultimately if PRP can increase the rate of tympanic membrane perforation healing thus negating the need for surgical intervention, PRP can potentially save the health care industry millions of dollars every year.

Specific Aim

The goal of our proposed prospective project is to investigate the efficacy of platelet enriched plasma (PRP) as a treatment for patients with chronic tympanic membrane perforation. Our primary outcome includes the prevention of patients requiring surgery for their perforation.

Inclusion Criteria

- Patients aged 18 or older
- Patients who have a chronic anterior tympanic membrane perforation that is <50% of the eardrum who meet criteria for tympanoplasty procedure
- Patients willing to comply with the protocol and attend all study visits.
- Patients is able to provide written informed consent

Exclusion Criteria

- Patients who are aged 17 or younger
- Patients who have previously undergone middle ear or lateral skull base surgery
- Patients who have a chronically draining ear who would not qualify for a tympanoplasty
- Any type of platelet disorder, cancer, or ongoing systemic infection.
- Any type of hemodynamic instability, septicemia, infection, tobacco use, any use of steroids to the ear drums, and patient unwilling to accept the risks of the procedure.
- Type I diabetes or other autoimmune pathology (based on case report by Kaux et al (2014) [11])

Benefits and Risks

There are some risks associated with a tympanoplasty, however, these risks are not associated with this study and will be covered in a separate consent for surgery.

There is a minimal risk for patients associated with the possibility for an unintentional breach of confidentiality. All records will be adequately protected to assure that this risk is minimized to the best of our ability.

Potential benefits of this study include the possibility of avoiding surgery for this subset of patients. This will decrease overall cost for the patient and avoid the inherent complications and pain associated with tympanoplasty surgery.

Study Procedures

During routine clinical care visits, the patients will be screened for selection according to the inclusion and exclusion criteria. Each patient matching these criteria and deemed eligible for the study by the study personnel will be approached for participation in the study. Study personnel will consent the patients in the clinic space behind closed doors. All patients will be given the opportunity to determine their interest in participation and ask any questions necessary to the study personnel. We will stress to the patient's that involvement in this study will not delay standard of care and will not delay or negatively impact eligibility for any type of surgical intervention. [name] is currently scheduling cases out by about 3 months, which is beyond the 6 week window we expect to complete this study. The only way involvement in this study will change any surgical plans is if PRP is able to successfully heal the tympanic membrane perforation.

This study consists of an initial visit, followed by three additional follow up visits. The initial visit may last up to one hour and will include consenting the patient for the procedure, a blood draw for PRP extraction, completing a short questionnaire (attached), history and physical, taking pictures of the perforation and application of the PRP. Patients will be scheduled for surgery approximately 5-8 weeks after their initial appointment. Prior to surgical intervention, they will be seen in clinic for follow up and given the same questionnaire (attached). The three additional visits will consist of shorter visits to evaluate the perforation size and need for surgery. Patients will be given compensation of \$10 for each visit they participate in in the study.

Patients will only be treated once with the PRP isolate. During the initial visit, the patient's blood will be drawn by study personnel. While the PI is completing other parts of the initial visit, the blood will be drawn in the clinic and centrifuged down into PRP in the clinic. This will take approximately 15 minutes. Please see below for step by step. We have also provided the Arthrex handout information sheet for PRP. The PRP has a gel-consistency that will be applied to the patient's tympanic membrane using a cotton tip swab.

After the five of the initial patients are treated we will review the treatment outcomes. Should all five fail to receive any benefit from the PRP treatment or if some other unanticipated serious adverse events emerges during the study the study team will consider the utility of moving forward. Given the history of the routine use of PRP in multiple other subspecialties including otolaryngology facial plastics surgery we do not anticipate any systemic or local reactions or problems. While this study is not without risks, patients are already scheduled for surgery at the time of enrollment. Participation in the study does not delay routine care in this patient population as surgery is universally scheduled 5-8 weeks after initial consultation. The likelihood of failure and/or success is not known and therefore stopping the study after 5 patients may prevent us from seeing the positive impact of this treatment. Prevention of even one out of 10 patients proceeding to surgery would be financially justifiable given the expense of surgery and the relative low cost of PRP treatment. After 10 patients are enrolled and treated the study team will again revisit the utility of proceeding with the study. At that point if no patients have any measurable benefit from the treatment the study will be stopped and carefully reviewed for futility.

Adverse events will all be documented using the CTCAE 4.0 Protocol and the PI will assess the association with the study drug. Any adverse events will be reviewed with the independent safety monitor who will have the authority to stop the study if the adverse events are associated with the investigational treatment and deemed a significant risk likely to occur in future participants. The standard serious adverse events of death, life-threatening complication, inpatient hospitalization or prolongation, or persistent or significant disability will all be considered events worthy of stopping the study. Again, this is an autologous therapeutic and there is no evidence of serious adverse events or adverse events beyond placebos or alternative therapies reported in the PRP literature for any of the approved uses.

Protocol for Preparation:

Each kit will contain the following: Double syringe, double syringe luer cap, tourniquet (disposable and latex free), alcohol pad, angel wing infusion set 19G, Gauze sponge (2x2in), Band-Aid (latex free), and patient label. All samples will be processed at KUMC in the ENT clinic.

Step 1: Prior to withdrawing, prime the outer and inner syringes by pulling each plunger completely back and forward before starting the process. Withdraw approximately 1.5ml ACD-A into the syringe. However, if the ACP is going to be used within 30 minutes of blood withdrawal, the use of ACD-A is not required.

Step 2: Blood withdraw. Place the tourniquet along the proximal arm and prep the skin where the desired vein to withdraw blood is located. Slowly withdraw by pulling back on the wings that are colored red. Fill the syringe with a maximum of 16cc of venous blood at a rate of 1cc every 2 seconds and seal the syringe with the red cap. Of note, blood will be collected with a single uninterrupted venipuncture with minimal damage to and manipulation of the donor's tissue. The 19 gauge butterfly needle will be used to withdraw blood, which is located in the kit.

Step 3: The centrifuge will be located in the clinic. Gently rotate the syringe in order to mix the blood and the ACD-A. Place the syringe into a bucket and an appropriate size counterbalance in the opposite bucket of the centrifuge. For the sake of this study, we will centrifuge the blood immediately upon collection. Recommendations are that it is done within 4 hours and stored at a temperature of 20 to 24 degrees Celsius.

Step 4: Run the centrifuge at 1500 rpm for 5 minutes. Remove the syringe, taking care to keep it in an upright position to avoid mixing the plasma and red blood cells.

Step 5: Transfer 4-7ml of the ACP from the larger outer syringe into the small inner syringe that comes with the kit. Slowly push down the outer syringe's red wings, while slowly pulling up the plunger of the small inner syringe. Final concentration of platelets is estimated around $600 \times 10^3 / \text{ul}$.

Step 6: Unscrew the small inner syringe. The ACP is ready for use at the point of care. The ACP can also be transferred into a sterile cup on the sterile field and transferred into a 10ml syringe for use. The ACP should be used within 4 hours after blood draw. For this procedure, we will use immediately after isolating.

Step 7: Once the ACP is isolated and ready to use it will be applied directly to the small tympanic membrane perforation with the use of the otomicroscope.

Patient follow up. We will ask patients to remain in the clinic for 30 minutes after the injection to assure the safety in the acute post-treatment period including bleeding, vertigo, ear fullness, pain, erythema, swelling, or other signs of inflammation or infection. We will conduct a phone interview between 3-5 days after application of PRP. During this phone interview conducted by study team members, we will again evaluate any concerning side effects with questions about the same issues mentioned above and any worsening of hearing loss or discomfort. Each subsequent follow-up visit will evaluate the safety of the treatment with the same endpoints and additionally include an assessment of efficacy.

The objective study outcomes will be in terms of success of healing of tympanic membrane, and pictures taken in clinic will be the data collected. The pictures taken of the perforation will be standardized to the size of the malleus in order to compare images between different visits.

Patients who do not have complete closure of the tympanic membrane will proceed to surgery as originally planned and resume routine follow-up. Should any patients achieve full closure and healing they will have their surgery cancelled and resume routine follow-up.

A full schedule of events for each study visit is included below.

Schedule of Events

	Treatment Visit	Post injection Follow up phone Call	Follow up Visit 1	Follow up Visit 2	Final Follow
	Day 0	Day 3-5	Day 14	Day 28	Day 42
Visits	1	N/A	2	3	4
Medical History and Current Medications	X				
Ringing in the Ear Evaluation	X	X	X	X	x
Overall Exam	X		X	X	x
Blood Samples	X				
Questionnaires	X	X	x	X	X
Hearing Test	X				X
Ear Exam	X		X	X	X
Eardrum Mobility Test	X				X
Balance Testing	X		X	X	X
Study Treatment Application	X				
Review Current Medications and Side Effects	X		X	X	X
Signs of Infection, edema, or Inflammation	X	X	X	X	X
Photographs of Eardrum	X		X	X	X
Approximate Study Visit Length (in hours)	2 hours	5-10 minutes	0.25 hour	0.25 hour	0.25 hour

While the principal investigator, [name], has had limited exposure to the use of PRP we as ENT residents have used it on a consistent basis during our facial plastics procedures. More specifically we apply it after rhytidectomy (face lift) to help with healing and decrease post-operative hematomas. We perform about 15-20 rhytidectomies a year. Furthermore, we will not have a control arm because those subsets of patients already exists in a day to day basis in the Neurotology clinic. The control arm would be standard patients that do not wish to participate in the study and simply wish to schedule surgery for tympanoplasty. Our aim with this initial study is to understand and evaluate the potential efficacy of platelet enriched plasma (PRP) as a treatment for patients with chronic tympanic membrane perforation. If preliminary data does suggest PRP may be beneficial, our next step is to perform a larger randomized prospective study.

Data Management and Security

To ensure the privacy and confidentiality of data collected from patients, data will be stored in REDCap, a password protected database accessible only by the relevant study personnel. No identifying information such as medical record number, date of birth or social security number will be collected.

Monitoring and Reporting Unanticipated Problems

The attached questionnaire will be utilized to identify any problems with the study that may be causing patient discomfort or problems. The results of these questionnaires will be discussed at regular meetings with the study personnel to determine to continue or discontinue the study. Any adverse events noted during the follow-up will also be reviewed. Any problems identified will be promptly reported according to the requirements of the KU Human Subjects Committee standard operating procedures.

This study will only be stopped prior to consenting all patients if there is a serious adverse event deemed to be connected with the application of the PRP. Patient's will be followed closely, including a follow up phone call 3-5 days post application, at the pre-arranged clinic visits, or at any point if a patient has significant concerns or symptoms. Multiple large systematic reviews and Cochrane data base reviews have found no associated complications with PRP compared to controls. However there are case reports with possible adverse events, including inflammatory reaction, in patients with autoimmune issues such as diabetes type I. In both the phone interview and clinic follow up we will ask and examine for any signs of excessive inflammation or reaction; specifically looking for erythema, drainage, swelling, edema, pruritus, or other inflammatory symptoms. After five subjects have been enrolled, we will look at cumulative adverse events and the number of subjects needed to proceed. We have appointed [name], a Neurologist, who will serve as an independent safety monitor to review any adverse events. If after five subjects or any other point the study is deemed unsafe or delaying standard of care, we will terminate the study.

Statistical Analysis Plan and Sample Size

Chi-square and Fischer exact tests will be used to test for whether or not patients were able to avoid surgery. Time to healing analysis will also be completed. Statistical significance will be based on an *a priori* designation of $p \leq 0.05$. Demographic variables and clinical variables will be summarized using descriptive statistics.

A minimum of 10 patients will be enrolled in this pilot study. Patients will not be randomized as a part of this study. Due to the pilot nature of this study and the absence of any prior data to build sample size calculations, this exploratory group should provide data for future studies and justify future sample size calculations.

Bibliography

1. Aggarwal, R., S.R. Saeed, and K.J. Green, *Myringoplasty*. J Laryngol Otol, 2006. **120**(6): p. 429-32.
2. Arora, N.S., et al., *Platelet-rich plasma: a literature review*. Implant Dent, 2009. **18**(4): p. 303-10.
3. Kristensen, S., *Spontaneous healing of traumatic tympanic membrane perforations in man: a century of experience*. J Laryngol Otol, 1992. **106**(12): p. 1037-50.

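### The planned chi-square and Fisher exact tests of avoiding surgery have no comparison group in this single-arm study; report one proportion with an exact 95% interval and a written success rule instead

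*Combined protocol and SAP*

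**What the plan says.** The Specific Aim sets the outcome: "Our primary outcome includes the prevention of patients requiring surgery for their perforation". The Statistical Analysis Plan and Sample Size section sets the analysis: "Chi-square and Fischer exact tests will be used to test for whether or not patients were able to avoid surgery", judged at p ≤ 0.05. The same section gives a minimum of 10 patients, without a calculation, and says: "Patients will not be randomized as a part of this study".

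The paragraph after the Schedule of Events says there will be no control arm. It describes who such patients would be (people who decline the study and simply schedule tympanoplasty), but no section plans to collect data on them.

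On what counts as avoiding surgery, Study Procedures says: "The only way involvement in this study will change any surgical plans is if PRP is able to successfully heal the tympanic membrane perforation". It describes follow-up this way: "The three additional visits will consist of shorter visits to evaluate the perforation size and need for surgery". The patient follow-up paragraph sends patients without complete closure to surgery and cancels surgery for those with full closure. It makes healing, recorded in clinic photographs, the objective outcome. Ear exam and photographs are both scheduled at Day 42, the final visit.

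On timing, Study Procedures gives two accounts. One is: "Patients will be scheduled for surgery approximately 5-8 weeks after their initial appointment"; the 5-8 week figure is repeated later in that section. The other says the surgeon is "currently scheduling cases out by about 3 months, which is beyond the 6 week window we expect to complete this study".

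**The concern.** A chi-square test of association or a Fisher exact test compares proportions between groups. Here everyone receives PRP, so the data form a single row: so many avoided surgery, so many did not. Nothing fills a second row. If the test is kept, whoever runs it must supply a comparator or a reference rate afterwards, and the p-value will depend on that choice. In an open, unblinded pilot the choice could be made after the results are seen.

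The proportion that would replace the test needs a counting rule. The protocol ties closure to cancelled surgery as a matter of care. It does not say how the analysis counts a patient who departs from that pathway, and it does not name the visit at which the outcome is judged.

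**Working it through.** **1. Inputs.** Groups: one. Patients: at least 10. Significance level: 0.05. Comparator data: none planned. Reference rate: none named for a test. The sample size has no stated calculation, so there is no plan figure to reproduce.

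**2. Can the named tests be run?** There are three ways to try.

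- *Borrowed comparator.* Assume 3 of 10 treated patients avoid surgery, and a comparator in which everyone is operated on. The Fisher probability of the observed table is C(10,3) divided by C(10+m,3), where m is the assumed comparator size.
  - m = 10: 120/1140 = 0.105. The mirror table is equally likely, so two-sided p = 0.21.
  - m = 20: 120/4060 = 0.030. The opposite extreme has probability 1140/4060 = 0.281 and is not added, so two-sided p = 0.030.
  - The treated data are the same, yet the result crosses 0.05 on the size of an invented group. These p-values only illustrate that dependence; they are not evidence about this trial.
- *Before against after.* All patients are scheduled for surgery at entry, so one could set 0/10 at baseline against x/10 afterwards. That uses the same patients twice in tests that assume independent groups.
- *Fixed reference.* A one-sample chi-square needs a stated rate. The Background quotes 12 to 63% success for paper patching but does not make it a benchmark. Zero does not work either: if the true rate is 0, the probability of one or more successes is 0, so a single success would always reject.

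**3. What the design supports.** For x successes among n treated patients, the Clopper-Pearson 95% limits are the 2.5% quantile of Beta(x, n−x+1) and the 97.5% quantile of Beta(x+1, n−x). With n = 10:

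| Successes | Rate | Exact 95% CI | Working |
|---|---|---|---|
| 0 | 0% | 0 to 30.8% | upper = 1 − 0.025^(1/10) = 0.308 |
| 1 | 10% | 0.3 to 44.5% | lower = 1 − 0.975^(1/10) = 0.003; upper from Beta(2, 9) |
| 2 | 20% | 2.5 to 55.6% | Beta(2, 9) and Beta(3, 8) |
| 3 | 30% | 6.7 to 65.2% | Beta(3, 8) and Beta(4, 7) |

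**4. The success rule.** The Specific Aim speaks of requiring surgery, Study Procedures says only healing changes the surgical plan, and the follow-up paragraph sends unclosed ears to surgery and cancels it for closed ones. Read together, for a patient who follows the plan, avoiding surgery is complete closure. Departures need a line of text:

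- 5-8 weeks is Day 35 to Day 56 (5×7 and 8×7). Surgery on Day 35 to 41 would precede the Day 42 visit, and a surgically closed membrane would then look like a success. The rule must say without prior surgery.
- A patient closed at Day 14 or 28, with surgery cancelled and returned to routine follow-up, might have no Day 42 visit. A strict Day 42 rule makes that patient a failure although surgery was prevented. Assume two patients closed at Day 42 and one such patient: the primary result is 2/10 (2.5 to 55.6%) and the sensitivity result is 3/10 (6.7 to 65.2%).
- With 10 patients, each reclassified patient moves the rate by 1/10, or 10 percentage points.

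**5. Timing.** About 3 months is roughly Day 91, or 91 − 42 = 49 days after the final visit. That cannot be squared with Day 35 to 56.

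**The case against.** The strongest reply is that this is an exploratory pilot meant to inform a later randomized study. No power statement depends on the test, and the protocol already makes avoiding surgery mean closure. Most of that stands. A reader might infer that the primary outcome is undefined, or that unhealed patients would be counted as successes. The documents do not support this: three sections read together point to closure, and the contrary reading takes one phrase of the analysis section on its own. Departures from the pathway are hypothetical. The documents give no rate for them, patients must be willing to attend all visits, and follow-up lasts six weeks.

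Three further inferences should be resisted.

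- The remark that preventing surgery in one patient of 10 would justify the expense concerns cost. It is not a success threshold, and the reviews after 5 and 10 patients ask about any benefit, so they do not turn on the counting rule.
- Of the 21 days from Day 35 to Day 56, 14 fall after Day 42. That is a share of calendar days, not of patients. Need for surgery, and whether it is cancelled, can still be judged at Day 42.
- Study Procedures also says of patients: "Prior to surgical intervention, they will be seen in clinic for follow up and given the same questionnaire". This need not mean an extra visit, since the schedule lists no fourth follow-up.

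The reply does not rescue the tests. Being a pilot explains a small sample; it does not give a two-group test a second group.

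**Conclusion.** The analysis named for the primary outcome cannot be carried out validly as written, because the study has no comparison group and plans no data for one. This follows from the text and needs no assumption about event rates. A single proportion with an exact 95% interval is what the design can give. At 10 patients the interval is wide (for 1/10, 0.3 to 44.5%), which is a fair statement of what the pilot can show.

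The counting rule is a clarification, not an error in the plan. Its importance depends on how many patients leave the pathway, which the documents do not say; the worked counts above are assumptions. The conflict between the two surgery-timing statements is real, and this review takes no position on which is right.

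**What to change.** In the Statistical Analysis Plan and Sample Size section:

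- Replace the chi-square and Fisher tests with the proportion of all treated patients who meet the primary outcome, with a Clopper-Pearson 95% CI. Drop the p ≤ 0.05 criterion for this outcome.
- Define success as documented complete closure without prior surgery, assessed at Day 42 from the ear exam and photographs already scheduled. The sponsor should write down how the two are combined if they disagree; requiring both to agree is one option, not a necessity.
- Keep every treated patient in the denominator. Count patients operated on earlier, unhealed but not operated on, or lost as not successes.
- List separately any patient with closure documented at an earlier visit and surgery cancelled but no Day 42 visit. Add a sensitivity analysis counting them as successes.
- Report actual surgery status descriptively.

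Add a matching sentence to the Specific Aim. Separately, the sponsor must reconcile the 5-8 week and 3-month statements in Study Procedures.

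Cost: text edits, with no new measurement for the primary outcome. Surgery status may need a later check if surgery falls after Day 42. The success rate may be slightly lower, because patients without documented closure at Day 42 are not successes, and no p-value is reported for the primary outcome.

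### The plan states two surgical waits, about 3 months and 5-8 weeks, and under the shorter one no rule puts the Day 42 assessment before surgery

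*Combined protocol and SAP*

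**What the plan says.** Study Procedures gives staff an assurance to stress when they approach a candidate: "involvement in this study will not delay standard of care and will not delay or negatively impact eligibility for any type of surgical intervention". The reason given is that the surgeon "is currently scheduling cases out by about 3 months, which is beyond the 6 week window we expect to complete this study". It adds: "The only way involvement in this study will change any surgical plans is if PRP is able to successfully heal the tympanic membrane perforation".

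The next paragraph of the same section gives another interval: "Patients will be scheduled for surgery approximately 5-8 weeks after their initial appointment". Further on, the section repeats the assurance on that second footing: "Participation in the study does not delay routine care in this patient population as surgery is universally scheduled 5-8 weeks after initial consultation". It also says that patients already hold a surgery booking when they enrol.

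On the order of assessment and surgery, Study Procedures says: "Prior to surgical intervention, they will be seen in clinic for follow up and given the same questionnaire". It also says: "The three additional visits will consist of shorter visits to evaluate the perforation size and need for surgery". The Schedule of Events puts the follow-up visits at Days 14, 28 and 42, with no visit windows. Photographs are taken at all clinic visits. The hearing test and the eardrum mobility test are done only at Day 0 and Day 42.

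The patient follow-up paragraph, after Step 7 of the preparation protocol, makes the clinic photographs the outcome data. Ears that have not fully closed go to surgery as planned, and surgery is cancelled for those that have. Specific Aim gives avoidance of surgery as the primary outcome. Statistical Analysis Plan and Sample Size announces a time-to-healing analysis without saying how surgery ends follow-up.

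**The concern.** Three months and 5-8 weeks are not two roundings of one wait. Both stand in the current text and both support the same assurance, but they have different consequences for the data. With a 3-month wait the whole study finishes before anyone is operated on. With 5-8 weeks the Day 42 visit falls inside the range of surgery dates.

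An ear operated on before Day 42 has had surgery, so it counts against PRP on the primary outcome. It does so after a shorter healing period than ears operated on later. It would also have no post-treatment, pre-surgery hearing or mobility value unless those tests were brought forward, because a Day 42 test would reflect the operation as well as the PRP. In the time-to-healing analysis, a drum closed by graft could be entered as healed, or the ear could be followed past the point where PRP alone can be judged.

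**Working it through.** **Inputs.** Surgical wait of about 3 months, surgery at about 5-8 weeks, and a 6-week study window (all Study Procedures). Visits at Days 0, 14, 28 and 42 (Schedule of Events). I take 3 months as 12-13 weeks and count 5-8 weeks from Day 0.

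**1. The plan's own window.** 6 × 7 = 42, which matches the Day 42 final visit.

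**2. Surgery dates under each interval.**
- About 3 months: 12 × 7 = 84 to 13 × 7 = 91, so Days 84-91.
- 5-8 weeks: 5 × 7 = 35 to 8 × 7 = 56, so Days 35-56.

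**3. Position of surgery relative to the final visit (surgery day − 42).**
- About 3 months: 84 − 42 = 42 to 91 − 42 = 49 days after the final visit. No operation precedes it.
- 5-8 weeks: 35 − 42 = −7 to 56 − 42 = +14. Surgery falls anywhere from 7 days before the final visit to 14 days after it. Operations on Days 35-41 precede it.

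**4. Healing period lost for an ear operated on in Days 35-41.** This depends on the last look before surgery, which the plan does not fix.
- If the ear is examined on the day of surgery: 42 − 41 = 1 to 42 − 35 = 7 days short.
- If the promised pre-surgery visit is the last scheduled visit before that date, Day 28: 42 − 28 = 14 days short.

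The Day 28 visit includes a photograph but no hearing or mobility test. A separate pre-surgery visit is described only as follow-up plus the questionnaire.

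**5. Room to avoid the clash.** Surgery on Days 43-56 lies after the final visit and within 5-8 weeks: 56 − 43 + 1 = 14 dates.

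**6. Starting day.** The initial appointment in one sentence naturally means Day 0, since it follows the description of the initial visit. The initial consultation in the other sentence is looser. If it came before Day 0, surgery could fall earlier still on the study calendar.

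**The case against.** The intended order can be seen in the text. Visits that judge the need for surgery, Day 42 among them, presuppose that surgery has not happened. Inclusion Criteria asks for willingness to attend every study visit. A clinic visit before surgery is promised. Unclosed ears go on to surgery and then routine follow-up, which reads as surgery after the study visits. If the 3-month wait is the true one, nobody is affected.

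Most of this stands, and it is why the point is minor. It shows intent but supplies no rule. For surgery on Days 35-41 the Day 28 visit would satisfy the promise of a clinic visit beforehand. A patient operated on at Day 38 could still attend Day 42, so the attendance criterion does not settle the order.

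A reader might also infer that the no-delay assurance is false, or that the study must postpone surgery. The documents do not support that. The assurance has a second basis, the 5-8 week interval itself, and participants operated on within that interval wait no longer than routine patients. Moving an operation from Days 35-41 to just after Day 42 would keep it within routine timing. It would conflict only with the statement that nothing but healing can change surgical plans.

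**Conclusion.** The point holds as a minor one. Study Procedures gives two incompatible surgical waits for the same assurance. Under the shorter one, surgery can precede the final assessment and cut the observed healing period by 1 to 14 days out of 42. The 14-day end assumes that Day 28 is the last look. The day counts treat an approximate 5-8 weeks as exact limits counted from Day 0.

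How many patients this touches is unknown and may be zero. Two stronger readings should be resisted:
- Seven of the 22 dates in Days 35-56 precede Day 42, and a reader might take that as the share of patients at risk. It counts calendar dates only, and the documents give no distribution of bookings.
- The plan remarks: "Prevention of even one out of 10 patients proceeding to surgery would be financially justifiable given the expense of surgery". A reader might conclude that one misjudged ear in 10 would cancel the plan's worthwhile effect. The remark is about cost and sets no efficacy threshold, and 10 is only the minimum enrolment.

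An ear's result would change only if it would have closed between its last look and Day 42, and the documents give no closure timing.

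**What to change.** 1. State one true surgery interval, counted from the PRP application (Day 0), and correct whichever of the two figures is wrong wherever it appears.
2. Require the final assessment (photograph, hearing test, mobility test) before surgery. Either book surgery after Day 42 within the 5-8 week window or, where an earlier date is fixed, carry out the full final assessment at the pre-surgery visit already promised.
3. In the analysis section, end time-to-healing follow-up at surgery, and report how many ears were operated on before Day 42. This needs the actual surgery date to be recorded.

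The cost is a few sentences and a date field. The trade-off is slightly less freedom in booking or, under the alternative, an earlier final assessment for some ears.
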